# 9.1.2 Serious Adverse Events (SAEs)

A serious adverse event is defined by ISO 20916 and/or 21 CFR 803.3 as an adverse event that:

- a. led to death
- b. led to serious deterioration in health that resulted in life-threatening illness or injury, resulted in permanent impairment
- c. life threatening (refers to any event in which the subject was at risk of death at the time of the event; it does not refer to an event which hypothetically might have caused death if it were more severe)
- d. required intervention to prevent permanent impairment/damage
- e. required inpatient hospitalization/prolonged hospitalization, or resulted in medical/surgical intervention to prevent life-threatening illness/injury or permanent impairment; or
- f. led to fetal distress, fetal death, or a congenital abnormality or birth defect
- g. important medical event that may require intervention to prevent one of the preceding conditions

# 9.1.3 Adverse Device Effect (ADE) / Serious Adverse Device Effect (SADE)

An adverse device effect is defined as any adverse event that is considered to be related to the use of an investigational medical device. This definition includes any event resulting from insufficiencies or inadequacies in the instructions for use, deployment, implantation, or operation or any malfunction of the investigational device (study device) and includes any event that is a result of a user error.

A serious adverse device effect (SADE) is defined as an ADE that has resulted in any of the consequences characteristic of an SAE.

# 9.1.4 Unanticipated (Serious) Adverse Device Effect (UADE/USADE)

An unanticipated (serious) adverse device effect (UADE/USADE) is any (serious) adverse device effect on health or safety or any life-threatening problem or death caused by, or associated with, a study device, which by its nature, incidence, severity, or outcome has not been identified in the current instructions for use and/or current version of the risk analysis report, or any other unanticipated serious problem associated with a device that relates to the rights, safety, or welfare of participants.

Page 50 of 67

UADEs/USADEs will be reported to FDA as required by 21 CFR Part 812.

### 9.2 Severity of Adverse Events

Each AE shall be assessed for its severity, or the intensity of an event, experienced by the participant according to the criteria below.

Severity Rating	Description
Mild	Event, signs, or symptoms that do not interfere with the participant's daily activity, are usually considered self-limiting, can be treated with non-prescription type medications, and do not require medical intervention
Moderate	Event may interfere or cause low level inconvenience with the participant's daily activity. Requires medical intervention and/or treatment; however, unlikely to require hospitalization or be considered potentially life-threatening in nature
Severe	Event may cause significant discomfort to the participant and/or interferes with the participant's daily activity. Requires medical intervention and/or treatment to preclude a permanent impairment; may be life threatening and/or require hospitalization

#### 9.3 Relationship of Adverse Event to Device(s)/Procedure

Each AE will be assessed for its relationship to the study device or procedure according to the following guidelines.

- A. Assess each AE for its relationship to the device or procedure.
  - Device Related: This category should be restricted to AEs directly attributable to any study device used during blood collection.
  - Procedure: A procedure includes any study-related activity performed during the participant's study visit.
- B. The following categories shall be used for assigning the certainty of the relatedness.

Relatedness	Description
Not Related	Event is independent of study intervention and/or evidence exists that the event is related to another etiology. There must be an alternative etiology documented by the clinician.
Unlikely Related	Event in which the temporal relationship to study intervention makes a causal relationship improbable (e.g., the event did not occur within a reasonable time of the study device use) and in which underlying disease provides plausible explanations (e.g.,

	the participant's clinical condition other concomitant			
	treatments).			
	Event in which there is evidence to suggest a causal relationship			
Likoly Polotod	and the influence of other factors is less likely. The event occurs			
Likely Kelaleu	within a reasonable time after use of the study device and is less			
	likely to be attributed to concurrent disease.			
Event in which there is clear evidence to suggest a c				
Dalatad	relationship and other possible contributing factors can be ruled			
Related	out. The event occurs in a plausible time relationship to use of			
	the study device and cannot be explained by concurrent disease.			

### 9.4 Reporting of Events

For all adverse events, all sections of the appropriate Case Report Form (CRF) must be completed.

- All SAEs, SADEs, and/or UADEs/USADEs must be reported to the Sponsor within one (1) working day of the site/investigator becoming aware of the event.
- De-identified copies of all requested relevant documentation should be submitted to the Sponsor within 72 hours of knowledge, as appropriate.

It is the responsibility of the Investigator to report adverse events to individual Institutional Review Boards (IRBs)/Ethics Committees (ECs) and/or regulatory authorities according to the local regulations in each participating country.

#### 9.5 Safety Committees

A safety committee will not be used.

#### 9.6 Device Deficiencies

The Investigator will record a device deficiency if a device used in the study procedure failed to meet its performance specifications whether due to mechanical failure, malfunction, or defect. Device deficiencies also include use errors and inadequate labeling. This applies to: devices used to treat the participant, or devices in which the package was opened, but the device was not used for treatment, or devices with which treatment was attempted, but the device did not remain through the entire study procedure/period.

Page 52 of 67

If the device deficiency was associated with an AE, the reporting provisions for AEs, ADEs, SAEs, SADEs and UADEs/USADEs apply.

Reported deficiencies will be investigated and reported under 21 CFR part 803 Medical Device Reporting by the Sponsor if necessary. The site may be contacted to provide additional information to allow the Sponsor to conduct a thorough investigation.

It is the responsibility of the Investigator to notify the IRB/EC of such device deficiencies in accordance with the IRB/EC and/or the Competent Authority's local regulations.

### **10 STATISTICAL METHODS**

The statistical analysis plan (SAP) will be finalized prior to database lock and will include a more technical and detailed description of the statistical analyses described in the following sections. This section includes a summary of the planned statistical analyses of the most important endpoints including primary and key secondary endpoints.

#### **10.1** Overview of Study Design

This is a prospective, multi-center random sample collection study designed to evaluate the clinical equivalence of the blood collection device with Test Device and EDTA tubes vs. respective comparators.

#### **10.2 Sample Size Considerations**

For clinical equivalence, 100 paired samples provide at least 90% power to ensure that mean biases and confidence intervals are within the clinically acceptable limits (CAL) at medical decision points, assuming no true bias between the tubes, residual SD, or  $CV \leq CAL$ , and collected data extend past the medically relevant points.

#### **10.3** Analysis Population

Safety analysis (summary of all device/procedure - related AEs) will be conducted on all enrolled participants.

All data collected will be reviewed for possible exclusion based on significant protocol deviations. Analysis will be performed on the resulting Per-Protocol (PP) dataset. Missing values will not be imputed and will not be included in any analyses.

Visual assessments: all collected tubes will be included in the summaries and analyses. For duration of sample collection, only tubes with complete fill will be included in the summaries and analyses.

Analytes: Pre-specified specimen exclusion criteria will be applied. Analysis will be performed on all first reported valid result unless a reason is provided for specific exclusions. Reasons for such exclusions will be included in the statistical report. If repeat tests are performed, a list of participants and tubes showing the initial and repeat results will be provided, showing which result is used in the analyses. For each investigational device vs. respective comparator device comparison, only participants with valid results in both tubes will be included in the bias analysis.

In addition, for study Part B, platelet analysis, a primary analysis of platelet results will be conducted excluding samples (from all tube types) with platelet flags confirmed with platelet clumps on smear review. Platelet flags and smear review data will be tabulated per tube type and sample type. An additional analysis will be done including all data, with and without platelet flags.

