Evaluation of the frequency of visual observations in the frequency of visual (Test Device EDTA tube) and all comparator tube types:	Frequency of selected visual observations (Table 4).
Evaluation of the frequency of occurrence of instrument flags (both asterisks and IP messages of interest) in the (Test Device EDTA) and all comparator tube types:	Frequency of occurrence of instrument flags. Confirmation of relevant flags by manual review of smears.

Page 23 of 67

Protocol	
----------	--

To evaluate peripheral blood smears for samples with platelet clump instrument IP messages.	
 
Frequency of occurrence of platelet clump instrument flags, confirmed by peripheral smear review.
 
Frequency of instrument platelet clump flags with no platelet clumps identified on peripheral smear.
 
	
To evaluate whole blood collection volume for the for the formation (Test Device EDTA)	Whole blood collection volume as measured by the weight of whole blood in the Test Device EDTA tube after collection.	
To evaluate duration of sample collection for the EDTA and capillary comparator-	Mean time in seconds between puncture timestamp and additive/blood mix start timestamp per tube type.	
Device Safety Assessment		
To assess the safety of the Test Device SST and EDTA systems.	Device/procedure - related adverse events (AEs).	
For Informational Purposes Only:		
SERUM		
Evaluate clinical equivalence between comparator tubes for the chemistry analytes listed in Table 3.	
 
Average difference for tube comparisons.
 
Test Device SST tube vs

	
EDTA		
Evaluate clinical equivalence between comparator tubes for all analytes listed in Table 5.	
 
Average difference between the following devices
 
Test Device EDTA tube vs.
 
EDTA vs.
 
EDTA vs.
 
EDTA
 
	

# Page 24 of 67

Protocol	
----------	--

CONFIDENTIAL

Protocol	Number:	
Version:	4.0	
Date: 07	Septembe	er 2022

• EDTA vs. EDTA	

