#### 5.4 Screen Failures

Screen failures are defined as participants who do not meet all eligibility criteria. Individuals who do not meet the criteria for participation in this study (screen failure) may not be rescreened.

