#### 7.1 Screening, Informed Consent, and Enrollment

Potential study participants will be screened against the inclusion and exclusion criteria outlined in Section 5. Participants will first be asked to provide written informed consent. Those who provide consent will be considered enrolled and will be assigned a unique participant number. Those meeting eligibility criteria will receive information regarding the study, including but not limited to test procedures, information to be collected, number and type of blood collection procedures, potential risks and benefits, and other pertinent information.

Part A	
Natural Sample Group:	
Contrived Sample Group:	
Part B	
Natural Sample Group:	
Contrived Sample Group:	
Blood Collection Procedure	
Natural Sample Group	
Study Part A:	one veninuneture using e
collect blood into a	tube. The collection
will be performed per the study site's	standard operating procedure for venipuncture. In
addition,	collections using
	. A

the Test Device system. The collection end time for each conventional and Test Device capillary tube collected from a participant will be noted on the CRF. For venous collections, the collection end time will be the time of the last tube collected from a venipuncture draw. Duration of collection for all capillary collections (conventional and Test Device) will also be captured

on CRFs as described in section 7.7 of this protocol, Supplemental Measurements, Visual Observations, and Analyte Testing. Study Samples will be mixed and processed per their respective IFUs.

Study Part B: For each participant,	one venipuncture
to collect blood into a	
tube. The collection will be performed per the study site's standard	ard operating procedure for
venipuncture. In addition, one one	e (1) conventional capillary
collection	tube.
	collection using the
Test Device EDTA	system. The collection end
time for each conventional	and Test Device
tube collected from a participant will be noted on the CRF. F	For venous collections, the
collection end time will be the time of the last tube collected	from a venipuncture draw.
Duration of collection for all capillary collections (conventional	and Test Device) will also
be captured on CRFs as described in the supplemental measurem	nents section section 7.7 of
this protocol, Supplemental Measurements, Visual Observations	, and Analyte Testing.

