#### 10.5.3 Safety Analysis Endpoints

A summary of all Device/procedure - related adverse events (AEs) will be provided.

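### Does a safety summary on all enrolled participants, with no stated split by collection method, fail to answer the Test Device safety objective?

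*Combined protocol and SAP*

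**What the plan says.** The safety objective in the section 3.1 table is worded for the investigational product: "To assess the safety of the Test Device SST and EDTA systems". Its endpoint is device- or procedure-related adverse events. The planned output in section 10.5.3 is one sentence: "A summary of all Device/procedure - related adverse events (AEs) will be provided".

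Section 10.3 sets the population: "Safety analysis (summary of all device/procedure - related AEs) will be conducted on all enrolled participants". Section 7.1 fixes who that is. Consent comes first, "Participants will first be asked to provide written informed consent", and it is sufficient: "Those who provide consent will be considered enrolled and will be assigned a unique participant number". Section 5.4 adds "Screen failures are defined as participants who do not meet all eligibility criteria", and no visible text takes such people out of the enrolled set.

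Two definitions bear on attribution. Section 9.3 says "Device Related: This category should be restricted to AEs directly attributable to any study device used during blood collection". Section 9.1.3 says "An adverse device effect is defined as any adverse event that is considered to be related to the use of an investigational medical device".

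Two general provisions also apply. Section 10.4 promises counts and percentages by device for visual and categorical observations. The introduction to section 10 describes itself as a summary and leaves technical detail to a SAP to be finalised before database lock.

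**The concern.** Two features look wrong.

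- **Population.** Someone who consents, fails eligibility and goes home is enrolled, and so sits in the safety set with no exposure to any device. Any event rate on that set would be diluted.
- **Attribution.** Every natural-sample participant is due both Test Device and comparator collections in the same visit. If the device-related category in section 9.3 covers comparators too, a single summary of device- or procedure-related events mixes bruising or syncope from the venipuncture with events from the Test Device.

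At stake would be whether the report answers the safety objective at all: a reader could see a total without knowing how much of it belongs to the investigational systems. Section 10.3 does state a split elsewhere (platelet flags by tube and sample type), so its absence for adverse events could be taken as deliberate.

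**Working it through.** The plan gives no adverse event rate, precision target or safety sample size, so there is no safety figure to reproduce. The check has three parts.

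**1. Size of the denominator effect.** Inputs: 100 complete data sets sought and at most 150 enrolled per part (section 4.1). The number unexposed, u, is not given and is assumed.

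- Unexposed share = u / (100 + u). For u = 0, 5, 10: 0%; 5/105 = 4.8%; 10/110 = 9.1%.
- Five participants with an event: 5/100 = 5.0%; 5/105 = 4.8%; 5/110 = 4.5%.
- Outer limit, if all 50 people between 100 and the cap of 150 were unexposed: 5/150 = 3.3%.

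The count is five in every case, and so is the listing. Only a percentage moves, and section 10.5.3 promises none.

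**2. How much of the collection activity is Test Device.** Part A has four capillary collections (section 7.4), two of them conventional (section 1.1), plus one venipuncture. Part B has two capillary collections, one of them conventional (sections 7.4 and 7.2), plus one venipuncture.

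| | Planned | With one repeat venipuncture |
|---|---|---|
| Part A | 2/5 = 40% | 2/6 = 33% |
| Part B | 1/3 = 33% | 1/4 = 25% |

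These are shares of collections. They are not expected shares of events, because risk per collection differs by method. They show that attribution matters, but they do not show that any safety result would be wrong.

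**3. Whether the text prevents attribution.**

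- Section 9.3 requires each event to be assessed for its relationship to device or procedure.
- The broad reading of study device in section 9.3 is not settled. The Study Device row of the synopsis lists the investigational-use tubes, section 9.1.3 glosses the investigational device as the study device, and comparators have their own section (6.2). With two Test Devices, the word *any* fits the narrow reading. On that reading, the device-related category already isolates Test Device events.
- On the broad reading, the adverse device effect definition in section 9.1.3 still isolates them, because it is tied to the investigational device.
- The by-device rule in section 10.4 does not name adverse events. If it covers them, the split by device is already promised. If it does not, no percentage is promised and part 1 has nothing to act on.
- Taking everyone from enrolment agrees with section 9.1.1, where event collection starts at enrolment. It ensures that no event is dropped.

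**The case for a change.** The strongest case for a change is that none of these provisions is a stated table. Neither section 10.3 nor section 10.5.3 names an adverse device effect output, section 10.4 does not mention adverse events, and a deferral to the SAP shows where the split could go without supplying it. Procedure-related events are the weakest spot: section 9.3 defines procedure as any study activity at the visit, and nothing visible divides those events by collection method. About 20 contrived-sample donors are also described as enrolled (section 4.1), and section 10.3 does not say whether they count. A line in the SAP would be cheap, and attribution is harder to rebuild afterwards if the event form does not record it.

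The factual part of this stands: the rule that consent alone enrols a person is real, and the layout is unspecified. It does not follow that the summary cannot isolate the Test Device, since nothing says methods are pooled and the definitions give a route to separation. The platelet comparison is weak, because a flag belongs to one tube, whereas an event such as syncope belongs to a participant who may have had several collections in one visit and often cannot be assigned to one of them. The donors' safety evaluation is placed in another document by section 7.11, so a natural-sample summary is the sensible reading.

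**Conclusion.** No change to the plan is needed. What is missing is the layout of a descriptive table, which analysts would be expected to fill sensibly in the SAP: events by part and attributed collection method, an entry for those that cannot be assigned, and any percentage taken over participants in whom the collection was started, with the number enrolled alongside.

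The population point brings no demonstrable gain. Its size rests wholly on an assumed number of unexposed people: nil if everyone who consents is collected, 5.0% against 4.5% with ten unexposed beside 100 exposed, and 3.3% at the cap of 150.

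The conclusion assumes that the relatedness coding is completed as section 9.3 requires and that the SAP supplies the usual event tables. Parts of the document are redacted, so a stated split may exist out of view.

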#### **10.4 General Considerations**

An alpha level of 5% will be used for all analyses. For equivalence testing with analytes having a CAL, this corresponded to obtaining 90% confidence intervals (associated with 95% two 1-sided tests).

For all analytes and continuous response metrics summary statistics including sample size, mean, standard deviation (excluding analytes), range of data obtained (minimum and maximum value) will be provided for each device.

For visual observations and categorical observations, number of observations and percent in each category will be summarized for each device.

#### Page 54 of 67

# 10.5 Analysis Methods

### **10.5.1** Clinical Equivalence Endpoints

For each analyte and each comparison, Deming regression (weighted Deming for analytes with percent CAL) or Passing-Bablok Regression will be used to estimate average differences between the investigational device and comparator device at medical decision levels (MDLs) for each analyte. Average differences with 95% confidence limits will be compared to the CALs to determine clinical equivalence between the devices.

### 10.5.2 Visual Observations and Supplemental Measurements Endpoints

The distribution of visual observation ratings for each tube type will be tabulated and summarized. No analysis will be performed on the visual observations data from this protocol alone; visual observations for Natural Samples from multiple protocols will be combined for analysis, as specified in a separate Meta-Analysis plan. For the Test Device a meta-analysis plan will assess for the Natural Samples the plasma free hemoglobin, serum volume, duration of sample collection, fibrin mass, complete barrier formation, and complete fill. For the Test Device EDTA, a meta-analysis plan will assess for the Natural Samples the whole blood volume, complete fill, duration of sample collection, and instrument flag frequencies.

#### 10.5.3 Safety Analysis Endpoints

A summary of all Device/procedure - related adverse events (AEs) will be provided.

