# **5 STUDY POPULATION**

#### Natural Sample Group

Participants will be recruited

in-person, via phone, or via electronic communications, such as social media, using IRB-approved recruitment materials. In order to cover the assay measurable range (AMR) additional in- and out- patient hospital populations with disease states such as the below listed conditions may be enrolled.

- Part A: Patients with hepatic, renal, endocrine, cardiovascular disorders and/or cancer.
- Part B: Patients with hematological disorders, cancers, diabetes and/or allergies.

Page 26 of 67

-- Protocol |

Protocol Number: Version: 4.0 Date: 07 September 2022

Approximately equal number of female and male participants with a targeted enrollment of at least 30% of either gender

. The patient disease state and gender will be documented on a CRF.

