### 9 ADVERSE EVENTS AND DEVICE DEFICIENCIES

#### 9.1 Definitions of Events

#### 9.1.1 Adverse Events (AEs)

An adverse event is defined as any untoward medical occurrence, inappropriate patient management decision, unintended disease or injury, or untoward clinical signs in participants, users, or other persons, with any connection to study related activities, whether or not related to the IVD medical device under investigation (ISO 20916). In this study, participant AEs are limited to those occurring immediately before, during, and immediately after specimen collection. Also, based on the nature of the study, test results will not be used for patient management decisions.

For the purpose of this study, Adverse events will be collected by the study team from enrollment through completion of the study (once discharged). If an adverse event occurs during this time the PI is required to follow-up with the participant. The clinical course of the event will be followed according to accepted standards of medical practice until the event resolves, stabilizes, or in the opinion of the Investigator, is no longer considered clinically significant. The Investigator must document the adverse event outcome on the AE CRF through a follow-up call to the participant.

Page 49 of 67

-- Protocol |

Protocol Number: Version: 4.0 Date: 07 September 2022

The participant may self-report any additional AEs that occur through 7 days post discontinuation by calling the site.

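### The safety summary covers only related adverse events, but the relatedness scale has no grade for plausible timing with an equally plausible disease cause, and the cut-off for related is not stated

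*Combined protocol and SAP*

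**What the plan says.** Three places define the safety output, and they agree. The safety endpoint in the section 3 table is related events. Section 10.3 reads "Safety analysis (summary of all device/procedure - related AEs) will be conducted on all enrolled participants". Section 10.5.3 reads "A summary of all Device/procedure - related adverse events (AEs) will be provided". The text supplied contains no table of all AEs and no table by relatedness grade.

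Collection is wider than reporting. Section 9.1.1 defines an AE as an untoward occurrence "whether or not related to the IVD medical device under investigation (ISO 20916"), and 9.4 requires a completed CRF for each one.

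Section 9.3 grades relatedness to device or procedure on four levels:

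- Not Related: "Event is independent of study intervention and/or evidence exists that the event is related to another etiology". The clinician must document the other cause.
- Unlikely Related: "Event in which the temporal relationship to study intervention makes a causal relationship improbable" "and in which underlying disease provides plausible explanations". The second condition is joined to the first by *and*, so both must hold.
- Likely Related: timing is reasonable, and concurrent disease is the less likely cause.
- Related: timing is plausible, and concurrent disease cannot explain the event.

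Section 5 allows recruitment of patients with hepatic, renal, endocrine or cardiovascular disorders or cancer in Part A. For Part B the text is: "Part B: Patients with hematological disorders, cancers, diabetes and/or allergies".

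**The concern.** When the summary is restricted to related events, the causality grade decides what is reported. The scale therefore needs a place for every event, and the summary needs a stated cut-off. The protocol has neither.

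The missing grade is the one for an event that follows the collection closely and that the participant's disease could equally well have caused. Section 2.2.1 lists syncope as a known effect of venipuncture, and Part A may enrol patients with cardiovascular disorders. A faint during or just after the draw in such a participant can have both causes in play. Two investigators could grade it differently, each with some textual support, and the reported result would differ.

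At stake is the completeness and reproducibility of the safety table. The study is open-label (6.5.2) and has no safety committee (9.5), so the protocol describes no independent review of the grading.

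**Working it through.** The plan gives no expected AE rate and no safety threshold, so there is no figure to reproduce. The check is logical: cross the two attributes that the 9.3 definitions use, then follow the event into the summary.

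**Step 1. Which grade fits?**

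| Timing | Disease explanation | Grade whose definition is met |
|---|---|---|
| Plausible | Less likely, or excluded | Likely Related or Related |
| Improbable | Plausible | Unlikely Related |
| Plausible | Equally plausible | None of Unlikely, Likely or Related; Not Related only if another cause is evidenced and documented |
| Improbable | Not plausible | None, unless judged independent of the intervention (Not Related) |

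The third row is the one that matters. Unlikely fails on timing. Likely fails because disease is not the less likely cause. Related fails because disease can explain the event.

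**Step 2. How often could the third row arise?** Section 9.1.1 confines participant AEs to the period around specimen collection, with self-report for up to 7 days (also 7.11). For events at the collection itself, timing will usually be plausible, so Unlikely is seldom properly available. What then places the event is the disease explanation. The documents do not say how many diseased patients will be enrolled, only that such patients may be added within the 100 to 150 participants per part. No count can be derived.

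**Step 3. Does the event reach the summary?** The cut-off is not stated, so take each possible one:

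| Grades counted as related | Event graded Not Related | Graded Unlikely | Graded Likely |
|---|---|---|---|
| Related only | Out | Out | Out |
| Likely and Related | Out | Out | In |
| Unlikely, Likely and Related | Out | In | In |

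Whether the same event is reported depends on a grade that the definitions do not settle and on a cut-off that the plan does not give. Under every cut-off, a Not Related grade removes it.

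**The case against.** The strongest reply is that the scale resists downgrading. A well-timed event cannot properly be called Unlikely, and Not Related requires the clinician to document another cause. An equivocal event may therefore drift up to Likely, and so into the summary under the natural reading of related. This stands: misgrading can go either way. A reader might infer that the gap systematically removes events, but the documents do not support that.

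A reader might also infer that the gap lies where most expected events fall, with a puncture-site hematoma in a patient with a hematological disorder as the example. That does not hold. The puncture causes the hematoma and the disease only predisposes to it. Section 9.3 grades relatedness to the procedure as well as the device, so Likely or Related fits. Syncope with cardiovascular disease is a sound example, but a narrow one.

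A third tempting reading is that events are lost. They are not: every AE is on a CRF, and all SAEs go to the sponsor within one working day whatever the cause (9.4). What may be lost is a line in the planned summary.

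Finally, section 10 describes itself as a summary and defers detail to a separate SAP, to be finalised before database lock. That SAP could contain an all-AE table and a definition of related. It is not in the text supplied, so the point is limited to what these documents commit to. A related-only endpoint and a four-grade scale are legitimate design choices. That does not answer the missing cut-off or the combination with no grade.

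**Conclusion.** The point holds in a limited form. The planned summary reports related events only, the scale has no proper grade for plausible timing with an equally plausible disease cause, and the cut-off for related is undefined. An event of this kind may be graded up or down, and if graded down it may be absent from the safety summary.

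The effect is probably small. This is a one-visit study that the protocol describes as minimal risk, and the safety analysis is descriptive. A reader might infer that regrading one or two events would overturn a safety conclusion, for instance by moving an upper confidence bound on the event rate. The plan sets no AE rate, bound or acceptance threshold, so no decision in it would change, and any event count used for such an illustration would be assumed.

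The conclusion rests on two assumptions: that at least some participants with a relevant disease are enrolled, and that the separate SAP does not already supply the table and the cut-off. The correction is still worth making, because the data will already have been collected and the repair costs almost nothing.

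**What to change.** In 10.5.3, tabulate all AEs by relatedness grade, with SAEs identified, and state which grades make up the related endpoint. Use the same definition in section 3 and in 10.3. This step alone keeps every event visible and needs no new data.

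In 9.3, add a possibly related grade, or a default rule, for an event with plausible timing where the collection and another cause are both plausible. Count it as related in 10.5.3. If the separate SAP is to carry the table, 10.5.3 should say so.

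Cost: one CRF option, a sentence or two of text and one extra table. The related-AE rate reported may be slightly higher. Sample size, blood collection and the equivalence analyses are untouched.
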